## 6 Statistical Plan

### 6.1 Sample Size Determination

Based on the practical issues of admission rate of preterm infants and capacity of temporal blood sampling at the Neonatal Department, we anticipate to include 200 preterm infants (< 32 weeks of gestation) with estimated rate of clinical chorioamnionitis of 15-20% (for overall preterm cases, 40-70% of premature PROM cases), and clinical LOS and/or NEC of 20-30%.

### 6.2 Statistical Methods

Infant grouping will be categorized based on the defined endpoints to compare: 1. Infants with vs. without chorioamnionitis; 2. Infants with vs. without LOS and/or NEC; 3. Infants with vs. without major mother's own milk feeding. Temporal data obtained from -omic analyses of blood and plasma samples collected every week will be analyzed by multivariate analysis with control for false discovery rates. Other data obtained from immune assays will be analyzed by univariate analysis. A panel of potential biomarkers will be identified by regression algorithm together with ROC analysis.

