### **5.3 Sample selection, analysis and comparison**

At the end of the study, the selection of appropriate samples for analysis will be conducted by all investigators of the study. Samples included in the analysis are those collected from birth until the disease diagnosis or completion of 4 postnatal weeks. In case of clinical diagnosis of LOS and/or NEC before completion of 4 weeks, further routine sample collection after diagnosis is continued if feasible.

Temporal samples will be analyzed to perform three separate comparisons:

- Infants without versus with LOS and/or NEC
- Infants without versus with clinical/histological chorioamnionitis
- Infants with major or minor amount of mother's own milk during the first two weeks of life ( $\geq$  or < 50% of feeding times as complete mother's own milk).

Plasma proteomic study will be prioritized and will include as many samples as possible, followed by validation with absolute quantification of potential proteins using immune assays. The type of other -omic analysis for plasma (miRNA profiling) whole blood (transcriptomics or epigenetics) as well as sample size will be decided depending on the results of proteomic study.

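### The immune-assay step is called validation, yet it apparently re-measures selected proteins in the same infants, and false discovery rate control is stated for the -omic data only

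*Protocol*

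**What the plan says.** Section 5.3 puts discovery by proteomics first, on all the samples that can be used. The immune-assay step comes after it, in these words: "followed by validation with absolute quantification of potential proteins using immune assays". The section does not say which infants or samples the immune assays will use. It also lists three comparisons: LOS and/or NEC, chorioamnionitis, and amount of mother's own milk.

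Section 1.1 applies both proteomics and immune assays to plasma from the study's 200 infants. Section 3.1 describes one cohort at one centre, sampled weekly from birth to four weeks or discharge. The size is a feasibility figure in section 6.1 ("Based on the practical issues of admission rate of preterm infants and capacity of temporal blood sampling at the Neonatal Department"). The document mentions no hold-out set, sample split, second cohort or external replication.

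Section 6.2 treats the two data types differently in adjacent sentences. The -omic data get multivariate analysis and a stated form of error control ("with control for false discovery rates"). The immune-assay data get only univariate analysis: "Other data obtained from immune assays will be analyzed by univariate analysis". A biomarker panel is then to be identified by regression and ROC analysis.

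**The concern.** There are two separate problems.

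**Validation in the same infants.** A protein goes forward because it differed between groups in these infants. If the difference was due to chance, a second assay on the same infants' plasma meets the same chance difference again. A small p-value there shows that the protein was measured consistently. It is not independent evidence that the protein is associated with the condition, and it takes no account of the selection. The word validation in 5.3 is not limited to measurement, so a reader of the results could credit the step with more than it delivers.

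**Uneven error control.** Proteomic and immune-assay results both serve the circulating-marker endpoints of sections 3.2 and 3.3. Section 6.2 states multiplicity control for one and not for the other, although the immune assays also run over several markers and three comparisons, and possibly over weeks.

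At stake is which markers are reported as validated and offered for the diagnostic panel.

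**Working it through.** The protocol gives no alpha, power, effect size, FDR level or number of proteins, so there is no figure of its own to reproduce. Inputs from the protocol are 200 infants, three comparisons and up to five weekly samples (birth to week 4). The expected case rates in 6.1 are "estimated rate of clinical chorioamnionitis of 15-20" per cent and "clinical LOS and/or NEC of 20-30" per cent, that is 200 × 0.15 to 0.20 = 30 to 40 infants and 200 × 0.20 to 0.30 = 40 to 60 infants. Thresholds, correlations, protein counts and effect sizes below are assumptions.

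**Step 1. Re-test of a falsely selected protein.** Let Z1 and Z2 be the discovery and immune-assay test statistics of a protein with no true association: bivariate standard normal with correlation r. With selection at two-sided level t and c = z(1 − t/2), the chance of a second p<0.05 in the same direction is

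P = 2 × P(Z1 > c and Z2 > 1.96) / t.

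| Selection | r = 0.5 | r = 0.7 | r = 0.8 | r = 0.9 | new infants (r = 0) |
|---|---|---|---|---|---|
| p<0.05 | 18% | 33% | 44% | 59% | 2.5% |
| p<0.01 | 28% | 53% | 71% | 90% | 2.5% |
| p<0.001 | 42% | 76% | 92% | 99.6% | 2.5% |

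The mildest case is about seven times the rate in new infants (18 / 2.5 ≈ 7). Stricter selection makes the re-test less informative.

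**Step 2. What share of confirmed proteins is false?** Step 1 is conditional on the protein being null. A simulation therefore took 500 proteins, 25 truly associated at a standardised difference of 0.8, 30 or 60 cases among 200 infants, Benjamini-Hochberg discovery at q = 0.05 or 0.10, and a re-test at 0.05.

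- Same infants: 61% to 69% of false discoveries are significant again at r = 0.7, and 95% to 98% at r = 0.9.
- Same infants: the false share among confirmed proteins is about 3% to 5% at q = 0.05 and 6% to 10% at q = 0.10. This is at or below the discovery FDR.
- New infants: the false share falls to 0.1% to 0.3%.

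**Step 3. Does FDR control on the re-test repair this?** Hardly. With 30 cases and q = 0.05, adding Benjamini-Hochberg to the re-test in the same infants moves the confirmation rate of false discoveries from 0.694 to 0.692 at r = 0.7, and leaves it at 0.983 at r = 0.9. The two problems therefore need different remedies.

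**Step 4. Multiplicity for an immune marker.** With k independent null tests at 0.05, the chance of at least one false positive is 1 − 0.95^k.

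- One marker, three comparisons: 1 − 0.95^3 = 0.143.
- One marker, three comparisons × five weeks: 1 − 0.95^15 = 0.537.
- Ten markers, three comparisons: 1 − 0.95^30 = 0.785, with 30 × 0.05 = 1.5 false positives expected.

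Weekly samples from one infant are correlated, so 54% is a ceiling. If the five weekly statistics within a comparison correlate at 0.3 to 0.7, and the comparisons are independent, the chance is about 50% to 38%.

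**The case against.** **Validation may mean measurement.** Absolute quantification on a second platform is a usual way to check relative proteomic signals, and the protocol's claims are modest: it speaks of potential biomarkers. No sentence says that p<0.05 on the immune assay confirms an association. This stands in part. The technical reading is plausible, but 5.3 does not limit the word to it.

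**Same infants is an inference.** This stands. It is nevertheless the only source of plasma that the document names.

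**Univariate describes the model, not the error control.** It contrasts with multivariate in the preceding sentence, and an analysis plan not shown could hold the adjustment. Nor does the protocol say that markers are tested week by week. Both are fair, and the 15-test figure is therefore only an upper case. What remains is that the protocol itself states FDR control for one data type and, in the next sentence, only univariate analysis for the other.

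**A stronger conclusion is tempting but unsupported.** A reader might infer that most validated markers would be false, or that the missing FDR control is what lets chance findings through. Step 2 speaks against the first: discovery FDR still bounds the false share. Step 3 speaks against the second: for preselected proteins, added FDR control changes almost nothing.

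**A hold-out is expensive.** With about 30 to 40 expected chorioamnionitis cases, setting infants aside would weaken discovery. This stands and limits the remedy.

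**Conclusion.** The point holds in two limited parts. First, as described, the immune-assay step is not independent validation of association. Over the assumed ranges, about 18% to 99.6% of falsely selected proteins would be significant again in the same direction, against 2.5% in new infants. The harm is that the step looks like strong evidence and adds little; it does not raise the false share above the discovery FDR. This rests on the inference that the same infants are used, and on assumed thresholds and correlations.

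Second, FDR control is stated for the -omic data only. For one null immune marker, the chance of at least one false positive is about 14% over three independent comparisons and at most 54% over fifteen tests; the latter assumes separate weekly testing, which the protocol does not specify.

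Both parts should be corrected, and the correction is cheap.

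**What to change.** - **Section 5.3:** call the step analytical (technical) verification, and state that its p-values are not counted as confirmation of association. State which infants' samples the assays use.
- **Section 6.2:** extend FDR control (Benjamini-Hochberg) to the family of immune-assay tests, preferably with one longitudinal test per marker and comparison in place of separate weekly tests.
- **Claims:** leave any statement of validated association to infants not used for selection. This does not require a hold-out or a new cohort in the present study.

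The cost is a change of wording and a routine adjustment, with slightly fewer nominally significant immune markers. No additional infants or blood are needed.

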## Study Summary

Title	Circulating markers in preterm infants with perinatal and neonatal inflammation: an observational study (NEOINFLAM)
Short Title	Markers for perinatal and neonatal inflammation
Study type	Observational study
Study Duration	18 months (October 2017-June 2019)
Study Center(s)	Single Center- Neonatal department, Bao'an Maternal and Child Health Hospital, Shenzhen, Guangdong, China
Objectives	The main objective of the study is to identify new circulating markers associated with early life inflammatory conditions in preterm infants including chorioamnionitis, late-onset sepsis and necrotizing enterocolitis in preterm infants during the first four weeks of life. The aim is to better understand these conditions, and more long-term, to provide earlier and better diagnosis.
Number of Subjects	200
Diagnosis and Main Inclusion Criteria	Inclusion criteria: preterm infants (< 32 weeks of gestation) Main diagnosis before and during the study: chorioamnionitis, late onset-sepsis and necrotizing enterocolitis

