## 1.1 Background

Every year, approximately 15 million infants are born preterm (< 37 weeks of gestation) and 1 million die (1). Preterm infants, especially those are born < 32 weeks of gestation, have immature gastrointestinal tract and innate immune system, which lead to high risks of development of necrotizing enterocolitis (NEC, a devastating intestinal disease affecting 7% preterm infants) and early life systemic infection (late-onset sepsis, LOS, up to 20-40% all hospitalized infants) (1,2). Those infectious diseases may lead to further long-term complications such as neurodevelopmental delay (1). NEC is very often related to LOS, possibly because an abnormal gut bacterial colonization and high gut permeability allow bacterial translocation (3). Conversely, a systemic inflammatory insult may predispose to NEC via impaired gut motility and immunity. As a result, in clinical trials, diagnostic markers are often used for combined LOS and/or NEC. Despite tremendous efforts to develop diagnostic markers for LOS and NEC, none of them are specific enough for clinical use (4). The current “gold standard” of blood culturing for diagnosis of LOS has many highly false negatives and is time-consuming whereas patients may develop septic shock and die shortly after clinical presentation. Ng et al performed a proteomic study to characterize protein biomarkers for LOS and NEC, but their work was exploratory without detailed focus on the mechanism based on an conventional LC-MS protocols (4). Recently, new mechanisms have been suggested to play role in the pathogenesis of adult sepsis such as circulating neutrophil extracellular traps (NETs), microparticles and miRNA but they have not been characterized in neonatal diseases (5,6).

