### 3 Study Design

#### 3.1 General Design

- This observational prospective cohort study includes 200 preterm infants, born < 32 weeks of gestation, at Neonatal Department, Bao'an Maternal and Child Health Hospital, Shenzhen, Guangdong, China.
- Patients, who fulfill inclusion criteria, will be recruited following the parental consent. The recruitment stops when the sample size reaches 200. Expected study duration: January 2017-June 2018.
- Patients will follow usual clinical procedures at the hospital. Patient groups will be categorized based on clinical records: infants born without and with clinical chorioamnionitis, infants without or with at least one episode of late-onset sepsis (LOS) and/or necrotizing enterocolitis (NEC).
- Enrollment and sampling are performed as indicated in the diagram below. Blood sampling is performed every week from birth until 4 weeks of age, or until discharge

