#### 3.2 Primary Study Endpoints

- Circulating markers in temporal postnatal blood samples associated with chorioamnionitis.

- Circulating markers in temporal postnatal blood samples associated with prognosis and/or diagnosis of neonatal LOS and/or NEC

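### Any reported panel AUC should be cross-validated with the selection inside the folds; read on the infants that selected the panel it would be too high, by an amount the protocol cannot fix

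*Protocol*

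**What the plan says.** - Section 3.1: "This observational prospective cohort study includes 200 preterm infants". Recruitment ends at that number, and the Study Summary names one centre.
- Section 6.1 bases the 200 on feasibility and expects a percentage of "clinical LOS and/or NEC of 20-30".
- Section 6.2 analyses the -omic data by "multivariate analysis with control for false discovery rates", analyses immune-assay data univariately, and then says: "A panel of potential biomarkers will be identified by regression algorithm together with ROC analysis". It does not say whether the FDR-controlled analysis comes before the regression, or on which infants the ROC curve is drawn.
- Section 5.3 says of the plasma proteomic study that it "will include as many samples as possible, followed by validation with absolute quantification of potential proteins using immune assays". It does not name the infants for the immune assays.
- Section 3.2 lists as a primary endpoint circulating markers "associated with prognosis and/or diagnosis of neonatal LOS and/or NEC".

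**The concern.** ROC analysis is part of choosing the panel, and there is one cohort to choose it in. Discovery draws on as much of that cohort as it can. The step that carries the word validation is a second measurement of individual proteins. Followed as written, nothing in the protocol tests the panel's discrimination outside the infants that selected it.

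An AUC computed on those infants reflects chance twice: in which proteins were picked and in how they were weighted. FDR control limits false single-protein discoveries. It does not adjust the AUC of a panel built from the survivors.

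The AUC is the figure a reader would set against the gap stated in section 1.1, that of existing markers "none of them are specific enough for clinical use", and against the longer-term aim in the Study Summary, "to provide earlier and better diagnosis". An inflated value would be carried into later diagnostic work. What is at stake is an accuracy figure, not the validity of a test of association.

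**Working it through.** **1. What the protocol gives.** The 200 is a feasibility number. There is no AUC, effect size, alpha or power to reproduce. Expected LOS and/or NEC cases: 200 × 0.20 = 40 and 200 × 0.30 = 60.

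**2. What has to be assumed.** The number of proteins, how many are informative, the size of their shift, the FDR level, the panel size and the regression method are not in the protocol. Base case: 300 proteins, 5 of them truly shifted by d SD, normal values, one sample per infant, two-sample t tests, at most the best 5 kept, logistic fit. In the screened setting, a Benjamini-Hochberg screen at 5% comes first.

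**3. Formulas.**
- One marker: AUC = Φ(d/√2), which gives 0.61 at d = 0.4, 0.64 at 0.5, 0.66 at 0.6 and 0.71 at 0.8.
- Fitted panel with weights w, true shifts δ and within-group covariance Σ: true AUC = Φ(w′δ / √(2 w′Σw)).
- Excess = mean apparent AUC on the selecting infants minus mean true AUC of the same panel, over the simulated runs in which a panel forms.

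**4. Results (600-1000 runs per setting; 40 cases / 60 cases).**

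| Shift | Panel forms, 5% FDR screen | Excess, screen first | Excess, no screen, best 5 |
|---|---|---|---|
| 0.4 SD | 31% / 51% | 0.122 / 0.090 | 0.205 / 0.161 |
| 0.5 SD | 60% / 83% | 0.091 / 0.070 | 0.155 / 0.105 |
| 0.6 SD | 89% / 98% | 0.069 / 0.047 | 0.099 / 0.060 |
| 0.8 SD | 100% / 100% | 0.029 / 0.018 | 0.033 / 0.018 |

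**5. Sensitivity.**
- With the screen, over 100-500 proteins and FDR 5-10%: 0.040-0.133 for 0.4-0.6 SD and 0.014-0.035 for 0.8 SD.
- Proteins correlated in blocks of 10 (r = 0.5): changes below 0.01.
- Lasso on all 300 proteins without a screen (80 runs): 0.25-0.26 at 0.4 SD, falling to 0.10-0.12 at 0.8 SD.
- In infants not used for selection, the expected excess is zero.

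**6. What cross-validation does.** Ten-fold, 3 repeats, screening and selection redone in each fold, 200 panels, screen first. Each cell shows 40 cases, then 60 cases.

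| Shift | Apparent / true / cross-validated AUC | Mean absolute error, apparent v cross-validated |
|---|---|---|
| 0.4 SD | 0.727 / 0.608 / 0.596; 0.713 / 0.619 / 0.610 | 0.119 v 0.068; 0.094 v 0.068 |
| 0.5 SD | 0.749 / 0.657 / 0.627; 0.756 / 0.688 / 0.664 | 0.092 v 0.079; 0.068 v 0.066 |
| 0.6 SD | 0.801 / 0.732 / 0.700; 0.817 / 0.767 / 0.744 | 0.069 v 0.062; 0.051 v 0.050 |
| 0.8 SD | 0.900 / 0.870 / 0.860; 0.901 / 0.883 / 0.878 | 0.035 v 0.035; 0.026 v 0.026 |

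Here the cross-validated value falls below the true one by 0.005 (0.883 − 0.878) to 0.032 (0.732 − 0.700).

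**The case against.** The strongest reply is that this belongs in a statistical analysis plan, which is not shown. How a panel AUC is internally validated is commonly settled there, and resampling may already be planned. Section 6.2 commits only to identifying a panel. It does not say that an apparent AUC will be reported. That stands: a reader might infer that the protocol plans to publish the AUC from the selecting infants, or that silence on cross-validation is itself an error. The text supports neither.

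A reader might also infer that the immune-assay step is offered as proof of the panel's accuracy. Section 5.3 does not say so. Its natural reading is confirmation of protein measurements, and section 6.2 analyses immune-assay data univariately. For that reason no figure is given here for a panel refitted on immune-assay values: the protocol describes no such refit. Nor does taking as many samples as possible for proteomics rule out other infants for the immune assays.

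It would be tempting to quote a single range for the inflation as a property of this trial. Only the 200 infants and the 40-60 cases come from the protocol. The rest is assumed, the order of the steps is unstated, and the model uses one sample per infant where the protocol collects weekly samples.

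The protocol also speaks of candidates and of association, sets no AUC target, and places better diagnosis in the longer term. By the figures above, cross-validation brings little gain in accuracy at 0.5-0.6 SD and none at 0.8 SD when a screen comes first.

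What the reply does not remove is that the protocol names no test of the panel's discrimination in infants outside the selection, and that a few sentences would supply an honest estimate.

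**Conclusion.** The point holds conditionally. If the panel AUC is read on the infants that selected the panel, it is biased upward, and FDR control on single proteins does not correct it. The protocol neither says nor excludes that this will be done.

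Under the base-case assumptions with 40-60 cases, the excess is about 0.02-0.03 for strong markers (0.8 SD) and 0.05-0.12 for weaker ones (0.4-0.6 SD) when a 5% FDR screen comes first and a panel forms. Keeping the best 5 without a screen raises it to about 0.2 at 0.4 SD. These figures illustrate the scale and cannot be derived from the protocol.

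This is a cheap improvement to the method, of minor to moderate importance, and not an error as written. Its main benefit is that a one-sided upward error no longer attaches to an accuracy figure tied to a primary endpoint.

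**What to change.** In section 6.2, state that any reported panel AUC will be estimated by repeated cross-validation, with every data-driven step (screening, selection, tuning, fitting) repeated inside each fold and all samples from one infant kept in the same fold. Report that AUC with an interval, beside the AUC on the selecting infants, and label the latter as apparent.

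In section 5.3, state whether the immune assays use infants outside the selection set. If they do not, do not present that step as validation of the panel's discrimination.

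The cost is wording and computing time, with no extra infants or assays. The reported AUC will be lower and slightly conservative, and the gain in accuracy is small when markers are strong and an FDR screen comes first.

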## 2 Study Objectives

[figure not shown]
**Primary objective:** To characterize circulating markers associated with the early life complications including chorioamnionitis, LOS and NEC in preterm infants during the first four weeks of life.

**Secondary objective:** To characterize how different feeding regimes and diets may affect these markers during the first four weeks of life in preterm infants

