### 5.2 Information in CRF

All collected data from clinical records will be recorded in the study CRF and feeding CRF by the study investigator at the hospital, including:

- Patient ID number
- Gestational age at birth
- Birth weight and gender
- Type of delivery: C-section or vaginal birth
- Diagnosis of chorioamnionitis:
  - Clinical or histological,
  - Gestational age at diagnosis,
  - Temperature, heart rate, plasma CRP and blood leukocyte counts of mothers at diagnosis
- Diagnosis of LOS and/or NEC:
  - Day of life at diagnosis,
  - Plasma CRP, total leukocyte counts
  - Clinical or culture-proven LOS
  - For culture-proven LOS: identified bacteria
  - Medical or surgical NEC

- Time of blood sampling and volume of blood samples
- Feeding details (in the Feeding CRF)
- Other notes: incidence of RDS, BPD, pneumonia

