## **9 Ethical Considerations**

This study is to be conducted according to applicable government guidelines and regulations and Institutional research policies and procedures.

This protocol and any amendments will be submitted to the Ethical Committee at Bao'an Maternal and Child Hospital, Shenzhen for formal approval of the study conduct. The decision of the Ethical Committee concerning the conduct of the study will be made in writing to the investigators.

All subjects for this study will be provided a consent form in Chinese describing this study and providing sufficient information for subjects to make an informed decision about their participation in this study. The consent form will be submitted with the protocol for review and approval by the Ethical Committee for the study. The formal consent of a subject must be obtained before that subject is submitted to any study procedure. This consent form must be signed by the subject or legally acceptable surrogate, and the investigator-designated research professional obtaining the consent.

Blood samples obtained for this cohort are left-over sample materials from routine clinical blood sampling for screening and diagnosis in preterm infants at the local hospital (Neonatal Department, Bao'an Maternal and Child Health Hospital, Shenzhen). Therefore, there are no potential harmful effects of blood sampling to the participating infants.

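### Section 5.2 lists infant CRP and leukocyte counts only at LOS/NEC diagnosis, so the listed data cannot show what the 6.2 panel adds to routine markers in non-cases or before diagnosis

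*Protocol*

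**What the plan says.** - **Aim and endpoint.** The Study Summary reads "The aim is to better understand these conditions, and more long-term, to provide earlier and better diagnosis". The primary objective in section 2 is "To characterize circulating markers associated with the early life complications including chorioamnionitis, LOS and NEC in preterm infants during the first four weeks of life". Section 3.2 adds, as a primary endpoint, markers associated with prognosis and/or diagnosis of LOS and/or NEC.
- **Panel.** Section 6.2 plans that "A panel of potential biomarkers will be identified by regression algorithm together with ROC analysis". It names no routine marker as comparator or covariate.
- **Samples.** Section 5.3 compares infants with and without LOS and/or NEC, on samples from birth up to diagnosis or the end of four weeks.
- **Data collected.** In section 5.2 the infant entry "Plasma CRP, total leukocyte counts" is a sub-item of the LOS/NEC diagnosis. The only other CRP and leukocyte entry is maternal, at chorioamnionitis diagnosis. For each blood sample, the list gives time and volume.
- **LOS definition.** Section 5.1 requires two or more of abnormal white cell count, low platelets, raised CRP and raised procalcitonin. Culture-proven LOS is clinical sepsis with a positive culture. Platelets and procalcitonin are not in the 5.2 list.
- **Source of blood.** Section 9 describes the samples as "left-over sample materials from routine clinical blood sampling for screening and diagnosis in preterm infants at the local hospital".

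**The concern.** A marker panel for diagnosis or prognosis is useful to the extent that it tells the clinician something that CRP and the blood count do not. Judging this requires routine values for cases and non-cases, from the same days as the research samples. The 5.2 list provides them for cases only, and only at diagnosis, which is where the sampling window in 5.3 ends.

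A regression and ROC step run without those values rewards any correlate of existing inflammation tests. The study could report a panel with a respectable AUC and be unable to say whether it adds to tests already done. False discovery rate control does not help here: it limits chance findings, whereas a protein that follows CRP is truly associated with the outcome.

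If whole-blood transcriptomics or epigenetics is run, which 5.3 makes conditional on the proteomic results, a second problem follows. Without counts in all infants, expression or methylation differences cannot be separated from differences in leukocyte numbers, and leukocyte count is one of the LOS criteria.

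**Working it through.** **1. The plan's own figure.** The sample size of 200 is a feasibility figure (section 6.1: "Based on the practical issues of admission rate of preterm infants and capacity of temporal blood sampling at the Neonatal Department, we anticipate to include"). No alpha, power or effect size is given, so there is no calculation to reproduce.

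**2. What the listed items cover.** Section 6.1 expects 200 infants "and clinical LOS and/or NEC of 20-30" percent.
- Cases: 200 × 0.20 = 40 to 200 × 0.30 = 60.
- Non-cases: 200 − 60 = 140 to 200 − 40 = 160.
- Infants with a listed CRP or leukocyte value: the 40-60 cases, at diagnosis only.
- Non-cases with a listed value: 0 of 140-160. Case samples before diagnosis with a listed value: none.

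A ROC curve for CRP or leukocytes needs values in both groups, as does a model of routine markers with and without the panel. Neither can be built from the listed items.

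**3. How a redundant marker would look.** The routine AUC and the correlation are assumptions; the protocol gives neither. Take normally distributed markers with equal variance in cases and non-cases. A routine marker with AUC A has standardised difference d = √2·Φ⁻¹(A). A candidate with within-group correlation r to it, and no other information on the outcome, has difference r·d and therefore AUC Φ(r·d/√2) = Φ(r·Φ⁻¹(A)).

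For A = 0.80, Φ⁻¹(0.80) = 0.8416:
- r = 0.5: Φ(0.421) = 0.663
- r = 0.7: Φ(0.589) = 0.722

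The Hanley-McNeil standard error, with q1 = A/(2−A) and q2 = 2A²/(1+A), is √{[A(1−A) + (n1−1)(q1−A²) + (n0−1)(q2−A²)]/(n1·n0)}, and z = (AUC − 0.5)/SE:

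| Candidate AUC | Cases/non-cases | SE | z |
|---|---|---|---|
| 0.663 | 40/160 | 0.051 | 3.2 |
| 0.663 | 60/140 | 0.044 | 3.7 |
| 0.722 | 40/160 | 0.049 | 4.5 |
| 0.722 | 60/140 | 0.042 | 5.4 |

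With a routine AUC of 0.75 to 0.85, the redundant candidate shows AUC 0.63-0.77 and z 2.6-6.8. Its added information is zero by construction, so this shows only how convincing such a marker can look when examined alone.

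**4. What a comparison could detect if the values were recorded.** Assume a two-sided 0.05 test, routine AUC 0.70-0.80, and correlation 0.3-0.7 between the two AUC estimates. With SE_diff = √(s1² + s2² − 2ρ·s1·s2) and power = Φ(ΔAUC/SE_diff − 1.96), over 40/160 to 60/140:
- AUC gain of 0.05: power about 14-44%
- AUC gain of 0.10: power about 43-96%

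An estimate with its interval is therefore a more realistic goal than a test.

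**The case against.** **Better diagnosis is a long-term aim.** This stands. Quoting only "to provide earlier and better diagnosis" could lead a reader to infer that the study undertakes to beat routine tests. The full sentence calls this a more long-term aim, the primary objective is to characterise associated markers, and no section claims superiority over CRP. For the mechanistic aim, a protein that tracks CRP can still be a valid finding. But section 3.2 makes markers of diagnosis and prognosis a primary endpoint and 6.2 plans a ROC panel, so interpreting diagnostic performance is within scope.

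**The comparison could be in an SAP.** This also stands: the absence of a comparison from 6.2 is not a finding on its own. An SAP can add a model, but it cannot supply values that were never transcribed.

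**The values may exist anyway.** The 5.2 list is introduced as an inclusive one, the CRF itself is an appendix not shown, the blood comes from routine testing, and the investigators hold the linkage key. The reading that added value cannot be shown at all is therefore too strong. What holds is that the listed items do not name these values for non-cases or before diagnosis. Leaving their capture unspecified invites incomplete or selective retrieval later.

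**The comparison is circular.** Largely right. CRP, white cells and platelets help define clinical LOS, and culture-proven LOS inherits those criteria. Recording more values does not cure this. The sampling window already set in 5.3 reduces it but does not remove it.

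**The illustration does not prove selection.** Correct. The number of proteins and the false discovery rate threshold are not given. At the weakest setting (z = 2.6, two-sided p about 0.010) selection among many proteins is far from assured.

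**Conclusion.** The point holds as a gap in data capture. On the items listed in 5.2, no infant routine value is named for any of the 140-160 expected non-cases, or for any case sample before diagnosis. The panel's gain over routine markers therefore cannot be estimated from the listed data, and a redundant marker could readily be selected.

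The case counts follow from the protocol's own rates. The AUC of 0.66-0.72 and z of 3.2-5.4 rest on an assumed routine AUC of 0.80, correlation 0.5-0.7 and normal markers, and are before false discovery rate control.

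The consequence is for interpreting the diagnosis and prognosis part of the primary endpoint and for the longer-term aim. The documents do not support reading this as a failed superiority claim, nor as proof that the information is out of reach. It is an inexpensive improvement that is best made before data collection.

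**What to change.** - **Section 5.2:** for every infant and each sampling day, record CRP and blood count (leukocytes with differential, platelets) wherever a routine value exists, and mark where none does.
- **Section 6.2:** report, with a confidence interval, what the panel adds to a base model of those same-day values plus gestational age and age at sampling, using the pre-diagnosis samples that 5.3 already selects.
- **Limitation to state:** CRP and counts help define both clinical and culture-proven LOS, so the comparison favours them, and the use of pre-diagnosis samples only reduces this.
- **If whole-blood transcriptomics or epigenetics is run:** use the counts to separate expression or methylation differences from differences in leukocyte numbers.

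Cost: transcription of existing laboratory values and one additional model. Some days will have no routine value, precision will be limited for small AUC gains, and the reported gain will be smaller than the stand-alone AUC suggests.
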